11.6 Pharmacodynamic Data

The whole blood collected for pharmacodynamic analysis following multiple doses of ARO-HBV at different dose levels will undergo analysis for changes in HBV-DNA, HBV-RNA (if scientifically feasible) and viral antigens based on reference laboratory (VIDRL) generated values. Cellular immunologic assessments will also be conducted (if scientifically feasible) at University of Auckland.

Immunology assessments (CHB patients in New Zealand only)

- Changes in profile from pre-dose to post-dose time points for: T cell subsets (activation and exhaustion state), NK cell subsets (activation and exhaustion state), B cell subset, monocyte subsets. To be conducted if scientifically feasible.
- Changes from pre-dose to post-dose time points for: HBV antigen specific T cell response (including HBcAg, HBsAg). To be conducted if scientifically feasible.

Virology assessments (CHB patients only)

- Virologic parameters will be summarized by cohort for the following:
- Quantitative HBsAg (qHBsAg): Log change from baseline to nadir and duration of response from nadir back to approximately 20% of baseline or EOS. In CHB patients who consent to additional follow up, HBsAg will be followed until the end of the additional follow-up period or early termination and summarized separately.
- Percent of patients with loss of HBsAg (defined as quantitative HBsAg < 0.05 IU/mL) at EOS and time to occurrence (Kaplan Meier). In CHB patients who consent to additional follow up,

HBsAg loss will be monitored until the end of the additional follow-up period or early termination and summarized separately.

- Percent of patients with anti-HBS seroconversion at EOS and time to occurrence (Kaplan Meier). In CHB patients who consent to additional follow up, anti-HBS seroconversion will be monitored until the end of the additional follow-up period or early termination and summarized separately.
- Change in Anti-HBs (quantitative) to EOS. In CHB patients who consent to additional follow up, change in Anti-HBs (quantitative) will be monitored until the end of the additional follow-up period or early termination and summarized separately.
- Quantitative HBV DNA (when quantifiable at baseline): Log change from baseline to EOS. In CHB patients who consent to additional follow up, HBV DNA will be monitored until the end of the additional follow-up period or early termination and summarized separately.

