- Quantitative HBV RNA: Log change from baseline to nadir and duration of response from baseline to EOS (if scientifically feasible). In CHB patients who consent to additional follow up, HBV RNA will be monitored until the end of the additional follow-up period or early termination and summarized separately.
- Quantitative HBcrAg: Log change from baseline to nadir and duration of response from baseline to EOS. In CHB patients who consent to additional follow up, HBcrAg will be monitored until the end of the additional follow-up period or early termination and summarized separately.
- Quantitative HBeAg (HBeAg positive only): Log change from baseline to nadir and duration of response from baseline to EOS. In CHB patients who consent to additional follow up, HBeAg will be monitored until the end of the additional follow-up period or early termination and summarized separately.
- Emergence of HBV mutations (sequencing of ARO-HBV target site, Core/pre-core, HBsAg epitope, any other mutations by deep sequencing) to EOS. In CHB patients who consent to additional follow up, HBV mutations will be monitored until the end of the additional follow-up period or early termination and summarized separately.

- Virologic response parameters may be summarized based on presence of interferon response gene SNPs (e.g. IL28B).

Descriptive statistics of virologic parameters will include mean, median, count, SD, minimum, and maximum. Additional details will be provided in the statistical analysis plan. If feasible, Clinical Study Report analysis of, quantitative HBsAg through EOS will be based on a final batched analysis of samples.

Separate analysis will be completed for all CHB patients receiving at least one dose, all HBeAg negative patients and all HBeAg positive patients, all treatment naïve and all entecavir or tenofovir experienced patients.

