## 11. VIROLOGY

Virology endpoints are only collected for CHB cohorts across the study period according to the protocol schedule of assessment. The analysis population for virology data is PD.

Virology endpoints will be analyzed separately for the main study (up to Day 113 EOS) and for the overall study duration, including the follow-up period, for the subset of patients that consented to participate in the follow-up. Endpoints will be derived separately for each analysis taking into consideration all the applicable data for the specific period.

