### Data Handling Rules

The units and lower limit of quantitation (LLQ) cut-off and imputed values in the table below will be used in all derivations and outputs.

Parameter	Qualitative / Quantitative	LLQ	Unit	Values for Imputation		
				< LLQ	< LLQ Detected	< LLQ Not Detected
HBeAg	Qualitative	0.22	PEIU/mL	N/A	N/A	N/A
qHBeAg	Quantitative	0.11	PEIU/mL	0.055	0.055	0.055 a)
HBV DNA	Quantitative	20	IU/mL	N/A	15	5
HBV RNA	Quantitative	1.65	Log10 U/mL	N/A	0.825	0.4125
qHBcrAg	Quantitative	1	kU/mL	0.5	N/A	N/A
qHBsAg	Quantitative	0.05	IU/mL	0.025	N/A	N/A

a) Values below 0.11 PEIU/mL may have been reported as 'not detected'

All reported qHBsAg and qHBcrAg results below the LLQ cut-off values will be treated as below LLQ and included in the '< LLQ' category counts.

qHBeAg results will be imputed based on the reported HBeAg (qualitative) results provided by the analyzing laboratory:

- Positive: All reported qHBeAg results equal to or above the LLQ cut-off value (0.11 PEIU/mL)
- '< LLQ': All results below the LLQ cut-off value where the HBeAg result is any outcome other than 'Not Detected'
- Negative: All results below the LLQ cut-off value where the HBeAg result is 'Not Detected'

HBV DNA results reported as 'Not Detected' will be imputed as 5 IU/mL. Results reported as 'Detected' or results below the LLQ cut-off value where the status is not specified ('Detect' or 'Not Detected') will be imputed as 15 IU/mL.

The quantitative HBV RNA results will be imputed based on the HBV RNA interpretation provided by the analyzing laboratory. If the interpretation is reported as 'LLOQ' and the result is below the LLQ cut-off value, the result will be imputed as 0.825 Log10 U/mL. Interpretations

reported as 'Negative' or results below the LLQ cut-off value where the status is not specified ('LLOQ' or 'Negative') will be imputed as 0.4125 Log10 U/mL.

Screening and baseline results below LLQ will not be imputed for any of the parameters and patients with results below the LLQ value at baseline will not be included in any of the post-dose summaries or the figures for the specific parameter.

Results equal to or above the LLQ cut-off value will be analyzed as reported, except where the result has been reported as a range ('> x' or '< y') in which case the result will be imputed to one significant digit above or below the reported cut-off value (i.e., '<30' will be analyzed as 29 and '>30.0' will be analyzed as 30.1).

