All results (except for HBV RNA) will be log transformed (base 10) for analysis purposes.

Imputed results will be identified in the data listings.

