### Time to Event Endpoints

- Time to HBsAg Loss is defined as the duration from first dosing to the date of HBsAg 'Not Detected' (HBsAg loss defined as HBsAg < 0.05 IU/mL). Subjects without HBsAg loss will be censored at the end of study (or the end of follow-up period).
- Time to anti-HBsAg seroconversion is defined as the duration from first dosing to the date of anti-HBsAg seroconversion. Subjects without anti-HBsAg seroconversion will be censored at the end of study (or the end of follow-up period).
- Duration of Response (for HBV DNA, qHBsAg, qHBeAg, qHBcrAg, qHBV RNA): defined as the duration from post dose nadir back to within 20% of baseline value. The analysis will only be performed for the overall study period (including the follow-up period) and only patients with baseline values above the LLQ for the specific parameter will be included in the analysis. Subjects with the endpoint not returning to within 20% of baseline value will be censored at the end of the follow-up period.

The time to event endpoints will be analyzed by survival analysis method. Survival analysis will only be conducted if there are at least some responders within a cohort. The survival functions of the time to event endpoints will be summarized for 25th percentile, median, and 75th percentile and their 95% confidence intervals. The rates of HBsAg Loss and anti-HBsAg seroconversion at Day 60 and Day 113 post dosing (and also at Days 169, 225, 281, 337 and 393 for the subset of CHB subjects that participated in the follow-up), the response rates (for HBV DNA, qHBsAg, qHBeAg, qHBcrAg, qHBV RNA) at Day 30 and Day 60 (and additional time points at 30 days intervals as appropriate) post nadir, and their respective 95% confidence intervals will be derived based on their survival functions estimated by Kaplan-Meier method. In addition, the graphs of Kaplan-Meier estimates of survival functions (survival plots) will be presented. Histograms will also be presented showing the response rates for each cohort over 30-day intervals.

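### qHBsAg duration of response ends at 20% of baseline in the protocol but within 20% of baseline in the SAP, and the SAP names no scale, so the cut-off can drift with baseline

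*SAP*

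**What the plan says.** **Protocol 11.6 (the synopsis has the same qHBsAg rule).** For qHBsAg the summary is the log change to nadir and "duration of response from nadir back to approximately 20% of baseline or EOS". Patients who consent to further follow-up are tracked to its end, or to early termination, and summarized separately. For HBcrAg the entry is "Quantitative HBcrAg: Log change from baseline to nadir and duration of response from baseline to EOS", with parallel wording for HBV RNA and HBeAg. HBV DNA has no duration endpoint: "Quantitative HBV DNA (when quantifiable at baseline): Log change from baseline to EOS". Further detail is left to the SAP.

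**SAP, Time to Event Endpoints.** One rule covers HBV DNA, qHBsAg, qHBeAg, qHBcrAg and HBV RNA: "defined as the duration from post dose nadir back to within 20% of baseline value". On the window: "The analysis will only be performed for the overall study period (including the follow-up period". Patients who do not return are censored at the end of follow-up.

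**SAP 11, opening text.** Virology endpoints are analysed separately for the main study to Day 113 and "for the overall study duration, including the follow-up period, for the subset of patients that consented to participate in the follow-up".

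**SAP, Data Handling Rules.** The units, quantitation limits and "imputed values in the table below will be used in all derivations and outputs". Those units are native except for HBV RNA, which is in log10 U/mL. The same section then says: "All results (except for HBV RNA) will be log transformed (base 10) for analysis purposes".

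**The concern.** Returning to 20% of baseline and returning to within 20% of baseline are different events. At the first a patient is still 80% suppressed; at the second the marker is nearly back where it started. A reader who holds the protocol and then reads the report cannot tell which of these ended the response.

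The missing scale makes this worse. A percentage of a concentration is the same fraction for everyone. A percentage of a log10 value is not, because the fraction depends on how high the baseline was. A programmer following the SAP could defend either scale for four of the markers, and for HBV RNA the literal reading is log10. Patients in one cohort could then have their response ended at quite different depths of suppression, and Kaplan-Meier curves would combine them.

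The window statement also conflicts with other parts of the SAP, so it is unclear whether a duration to Day 113 is produced for all CHB patients.

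**Working it through.** The plan gives no figure to reproduce; this is a comparison of definitions.

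**1. Threshold, untransformed values**
- Protocol, 20% of baseline: log10(0.20) = −0.699, or 0.70 log10 below baseline.
- SAP, within 20% of baseline, approached from below: log10(0.80) = −0.097, or 0.10 log10 below baseline.
- Gap: 0.699 − 0.097 = 0.602 log10; 0.80 / 0.20 = 4-fold.
- At a baseline of 1,000 IU/mL, the response ends at 200 IU/mL (protocol) or 800 IU/mL (SAP).

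**2. The same SAP rule on log10 values**

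For a baseline B above 1 unit, the lower limit is 0.8 × log10(B). As a share of baseline that is B^0.8 / B = B^(−0.2).

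| Marker and baseline | Share of baseline at cut-off |
|---|---|
| qHBsAg 5 IU/mL (screening minimum, protocol 7.2) | 5^(−0.2) = 72% |
| qHBsAg 1,000 IU/mL | 1,000^(−0.2) = 25% |
| qHBsAg 100,000 IU/mL | 100,000^(−0.2) = 10% |
| HBV RNA 3 log10 U/mL | 10^(−0.6) = 25% |
| HBV RNA 5 log10 U/mL | 10^(−1.0) = 10% |

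On native values every row would be 80%. Apart from the screening minimum, the baselines are chosen for illustration.

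**3. Does any passage fix the scale?** The general log10 instruction is the nearest to an answer. Against it, the table of mostly native units is said to govern all derivations, and the duration rule itself compares baseline with the quantitation limit. For HBV RNA, Data Handling Rules exempts it from log transformation, while the quantitative assessments text lists it among the markers to be log transformed. The duration rule names no scale.

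**4. Window**
- Time to Event Endpoints: overall period only.
- SAP 11 opening: main study and overall period separately.
- SAP 17.3: PD analyses at Day 113 and again after follow-up.
- SAP 19: all five duration tables (14.2.4.6 to 14.2.4.10) are marked for the Day 113 interim.
- SAP 21: the duration plots and histograms are labelled as follow-up outputs.
- Protocol 11.6: qHBsAg duration to EOS, plus a separate follow-up summary.

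The first item cannot stand with the second, third and fourth as written.

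**5. What the threshold gap could mean in days (assumed rates)**

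The documents give no rebound rate. With a log-linear rebound of r log10 per 28 days, the time between the two crossings is 0.602 / r × 28: 169 days at r = 0.1, 84 at 0.2 and 56 at 0.3, for any nadir deeper than 0.70 log10. Not all of this could be observed. Take an assumed nadir of 1.5 log10 at Day 85 and r = 0.1:
- 20% is reached after (1.5 − 0.699) / 0.1 × 28 = 224 days, at Day 309.
- 80% is reached after (1.5 − 0.097) / 0.1 × 28 = 393 days, at Day 478, beyond the last visit at Day 393.
- The observable difference is 393 − 309 = 84 days.

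Follow-up visits are 56 days apart, so the 56-day case is one visit.

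**The case against.** The best defence is that the protocol's phrase is loose wording for within about 20%, that the log10 instruction answers the scale question, and that duration is a minor descriptive summary for which listings and individual plots let a reader apply any cut-off. The first part is possible but unconfirmed. The second would settle the scale only by making the cut-off depend on baseline. The third stands and limits the weight of the point.

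Several stronger readings are tempting, and the documents do not support them:
- **The SAP swaps a short window for a long one.** Protocol 11.6 also follows qHBsAg through additional follow-up. What is unclear is the Day 113 version.
- **The SAP drops the Day 113 duration.** The word *only* suggests so, but SAP 11, 17.3 and 19 point the other way. This is an internal conflict, not a proven omission.
- **The SAP overrides the protocol for the other four markers.** For HBV RNA, HBcrAg and HBeAg the protocol names no event that ends response and leaves detail to the SAP. HBV DNA duration is an addition.
- **The HBcrAg result depends on a free choice of unit.** The SAP fixes kU/mL.
- **Censoring credits unobserved time to patients who leave early.** Protocol Table 1.5 schedules these markers at early termination, and the SAP does not impute missing data. Censoring at the scheduled end would be a strained reading.

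**Conclusion.** The point holds on two matters. The protocol and SAP thresholds for qHBsAg differ 4-fold (0.60 log10) as written. The SAP's 20% has no stated scale; on log10, which is the literal reading for HBV RNA and an available one for the rest, it is a different fraction of baseline for each patient. The drift over the illustrated baselines is from 72% to 10% for qHBsAg and from 25% to 10% for HBV RNA. The SAP's statements on the window also need to be made consistent.

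The threshold and scale results are plain arithmetic on the text. The differences in days rest on assumed rebound rates and nadirs, are partly unobservable within follow-up, and should not be quoted as expected effects. Duration is not a named objective, and SAP 2.4 says the cohorts are not meant for hypothesis testing. The consequence is confined to five tables, five Kaplan-Meier plots and five histograms. It should be corrected, but it does not threaten the study's main conclusions.

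**What to change.** In the SAP's Time to Event Endpoints:
1. Define return as a fixed log10 distance below baseline, the same for every marker including HBV RNA: 0.10 log10 for within 20%, or 0.70 log10 for 20% of baseline.
2. Reconcile with protocol 11.6 by naming one distance as main and reporting the other as sensitivity. SAP 17.2 records that an interim on all data to Day 113 was completed in February 2020, so the report should say that this choice was made with data already seen.
3. Replace the *only* statement with a clear one: whether a duration to Day 113 for all CHB patients is produced alongside the follow-up one, and who is in each.
4. As a clarification, censor at each patient's last non-missing sample of that marker, including the early-termination sample.

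The cost is SAP wording, some reprogramming of the duration outputs and one extra sensitivity output. No new data are needed.

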#### Quantitative assessments: HBV DNA, qHBsAg, qHBeAg, qHBcrAg, qHBV RNA, anti-HBsAg and ratio of bound/free anti-HBsAg (if available)

Quantitative HBV DNA, qHBsAg (overall and by IL28B genotype mutation [rs12979860 and rs8099917]), qHBeAg qHBcrAg and qHBV RNA will be logarithm (log 10) transformed, and the observed log transformed value and change from baseline of the log transformed value will be summarised descriptively for all time points assessed. In addition, for HBV DNA, qHBsAg, qHBeAg, qHBcrAg, and qHBV RNA, the change to the maximum post-dose decline (nadir) from baseline will be pooled for a nadir 'visit' and summarized by cohort as well. The nadir values will also be calculated based on the overall study period (including the follow-up visits). The ratio of bound/free anti-HBsAg will be summarized descriptively without log transformation. The change from baseline values at each post-baseline visit will also be categorized ('<0.5 log decline', '0.5-<1.5 log decline', '1.5-< 3 log decline', '> 3 log decline') and summarized. Only patients with a baseline result above the LLQ for the specific parameter will be included in the post-baseline summaries.

The summary table will also be repeated for the following subgroups (based on the categories described for the qualitative assessments below):

- Baseline HBV DNA:
  - Baseline HBV DNA Not Detected
  - Baseline HBV DNA Detected

- Baseline HBeAg:
  - Baseline qHBeAg Negative
  - Baseline qHBeAg Positive

The quantitative HBV DNA, qHBsAg, qHBeAg, qHBcrAg and qHBV RNA over time (up to Day 113) will be plotted for mean and individual subject values, based on log transformed data, by cohort. The log transformed results will be plotted on a linear scale (y-axis). The log transformed LLQ values will be added as a horizontal reference line. The change from baseline values will also be presented. The plots will also be presented for the subset of CHB patients that participated in the follow-up period and will include all available data. Only patients with a baseline result above the LLQ for the specific parameter will be included in the plots.

Qualitative assessments: HBV DNA, HBV RNA, HBsAg Loss, anti-HBsAg, HBeAg and anti-HBeAg

The quantitative HBV DNA results will be categorized as follows for the qualitative HBV DNA summary:

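### Duration of response runs from each patient's nadir with no minimum decline, so a nadir at the last visit is censored at day 0 and most non-responders count as losing a response

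*SAP*

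**What the plan says.** SAP section 11, Time to Event Endpoints, covers HBV DNA, qHBsAg, qHBeAg, qHBcrAg and HBV RNA.

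- **Clock and event:** the duration is "defined as the duration from post dose nadir back to within 20% of baseline value".
- **Entry:** "only patients with baseline values above the LLQ for the specific parameter will be included in the analysis". No decline is required.
- **Censoring:** "Subjects with the endpoint not returning to within 20% of baseline value will be censored at the end of the follow-up period".
- **Reporting:** Kaplan-Meier response rates are read "at Day 30 and Day 60 (and additional time points at 30 days intervals as appropriate) post nadir".
- **Cohort condition:** "Survival analysis will only be conducted if there are at least some responders within a cohort". A responder is not defined for this endpoint.

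Under Quantitative assessments, the same SAP section takes the nadir as the largest post-dose fall from baseline, and also derives it over the whole study including follow-up. It sets no minimum fall. That paragraph sorts by-visit declines into bands whose lowest boundary is 0.5 log, but nothing links the bands to duration of response.

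Protocol 11.6 also starts at the nadir for HBsAg: "Log change from baseline to nadir and duration of response from nadir back to approximately 20% of baseline or EOS". For HBV RNA, HBcrAg and HBeAg, however, it runs duration from baseline to EOS, and for HBV DNA it lists no duration. The SAP applies the nadir start to all five.

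**The concern.** A duration of response should begin when a response begins and should be computed in patients who had one. Here it begins at the deepest point, in anyone measurable at baseline. Three things follow from the text:

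1. If the lowest value is the last one, start and censoring coincide, and the patient informs no later Kaplan-Meier estimate.
2. If a patient is suppressed at a steady level, assay noise decides which visit is the nadir, and the suppressed time before it is discarded.
3. A patient with no response still has a lowest value. It either lies inside the 20% band already or is followed by one that does, so the patient is counted as losing a response that never occurred.

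Late nadirs are plausible. The Version 3.0 summary of changes says follow-up was added because antiviral effects of earlier siRNA compounds continued six months or more after the last dose. SAP 2.4 says results will feed sample-size calculations for later studies, and a curve that mixes non-response with rebound is a poor input.

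**Working it through.** The documents give no event count or expected rate for this endpoint, so there is no plan figure to reproduce. The rule was applied literally to assumed patients on the 13 post-dose virology visits of Protocol Tables 1.2 and 1.5: Days 8, 15, 29, 43, 57, 71, 85, 113, 169, 225, 281, 337 and 393.

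**Event threshold.** On the raw scale, within 20% of baseline means a change no lower than log10(0.8) = -0.097 log. If the band is taken on the log10 value, leaving it needs a fall of 0.2 × log10(baseline): 0.14 log at 5 IU/mL, 0.40 at 100, 0.60 at 1000 and 0.80 at 10000. The SAP does not say which scale applies.

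**Nadir at the last visit.** Duration = 393 - 393 = 0, censored. This holds on either scale.

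**Effect of mix.** Assume 8 patients. One has its nadir at Day 85 and is back at baseline at Day 281 (event at 281 - 85 = 196 days). Of the other seven, who never rebound, k have their nadir at the last visit and 7 - k are followed beyond Day 200 after nadir. At day 196 the risk set is 8 - k, so the Day-200 rate is 1 - 1/(8 - k).

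| k | Day-200 rate |
|---|---|
| 0 | 7/8 = 88% |
| 2 | 5/6 = 83% |
| 4 | 3/4 = 75% |
| 6 | 1/2 = 50% |
| 7 | 0% |

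In every row 7 of 8 patients never rebounded.

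**Plateau.** Assume a steady -1.5 log from Day 85 to Day 393: 393 - 85 = 308 suppressed days over seven visits. With independent noise each visit is equally likely to be lowest, giving durations of 308, 280, 224, 168, 112, 56 or 0 days. The median is 168 days, and the chance of 0 is 1/7 = 14%. The size of the noise does not matter.

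**Non-responders.** Assume true change 0, independent normal assay error and the raw-scale band. The assay SD is not in the documents, so it was varied from 0.03 to 0.15 log, with and without error in the baseline value. Allowing the event at the nadir visit, about 87% to 99% become loss-of-response events. If the event must come after the nadir visit, a nadir at the last visit cannot be an event, so the share is at most about 12/13 = 92%. The share at day 0, without baseline error, is [1 - Φ(-0.097/SD)]^13: 99% at SD 0.03, 21% at 0.08 and 2% at 0.15. With baseline error it is 35% at SD 0.08.

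**A mixed cohort.** Assume 8 patients with baseline 1000 IU/mL: two still falling at Day 393, two with nadir at Day 113 and sustained, two with nadir at Day 113 and rebounding after 168 and 224 days, and two non-responders with changes of 0.05 log or less. Raw band:

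| Rule | 30 d | 60 d | 180 d | 250 d |
|---|---|---|---|---|
| SAP, event allowed at nadir visit | 0.75 | 0.75 | 0.56 | 0.38 |
| SAP, event only after nadir visit | 0.67 | 0.67 | 0.50 | 0.33 |
| Clock from first fall of at least 0.5 log, responders only | 1.00 | 1.00 | 1.00 | 0.83 |

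Under the SAP rule the non-responders supply 2 of the 4 events, at day 0 or day 14, and both fallers are censored at 0. In the last row the fallers are censored at 350 and 336 days. Its days run from first response, so the rows differ in time origin as well as in membership.

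**The case against.** **The wording could be read more kindly.** Coming back to the band may imply having left it, which would remove day-0 events. The SAP does not say so, and does not say what happens to patients who never left. The cohort condition does not help: it decides whether a cohort is analysed and removes no individual patient.

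**The protocol chose the nadir start.** True for HBsAg, and that stands: the from-nadir figure should still be reported. It does not hold for the other four markers.

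**The endpoint is descriptive.** This also stands. Duration is in no study objective, and SAP 2.4 disclaims inference. The SAP plans log change by visit, decline categories, mean and individual plots through follow-up, and time-to-event listings. A reader might infer that durability across doses would be misjudged overall. The documents do not support that, because a still-falling patient is visible in those other outputs.

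**Late responders are not all lost.** A reader might infer that the rule removes exactly the patients follow-up was meant to capture. It does not. Six months after a Day 57 dose is about Day 240, leaving 393 - 240 = 153 days of follow-up; after a Day 15 dose it is about Day 198, leaving 195. A nadir there still contributes time. Only a nadir at the final visit gives zero.

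**The numbers are assumed.** Correct. The 0% needs 7 of 8 patients at their lowest value at the last visit, and the day-0 share of non-responders swings too widely to quote as one figure. The high overall event share among non-responders is robust over the SDs tried.

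**Conclusion.** The point holds: this is a stated rule that, followed exactly, produces a misleading Kaplan-Meier rate. Zero duration for a last-visit nadir follows from the text alone when censoring is at that visit. The plateau loss needs only independent noise. The 87% to 99% for non-responders rests on a raw-scale band and the assumed SD range. The shift in the response rate depends on the mix and can be small (83% against 88%) or total.

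The consequence is limited to SAP Tables 14.2.4.6 to 14.2.4.10 and Figures 14.2.8.3 to 14.2.8.12. No type I error or power is involved, and the secondary objective (HBsAg decline to nadir) is untouched. Within those outputs it matters, because cohorts have 4 to 8 patients, or at most 4 in Cohorts 6 to 11 (12 in Cohort 12), so one patient classified wrongly moves a rate a long way. It should be corrected before the final analysis.

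**What to change.** In SAP section 11:

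1. **Responder.** Restrict the Kaplan-Meier set, per marker, to patients with a fall of at least 0.5 log10 from baseline or a post-dose result below LLQ. The second limb is needed because of the imputed values: HBcrAg below LLQ is set to 0.5 kU/mL, so baselines of 1.0 to 1.58 kU/mL (0.5 × 10^0.5) cannot show a clear 0.5-log fall. HBV DNA below LLQ but detected is set to 15 IU/mL, so neither can baselines of 20 to 47 IU/mL.
2. **Start.** The first visit meeting that definition.
3. **End.** The first later visit meeting the return criterion, with its scale stated and reconciled with the protocol wording. On a log10 band, a 0.5-log fall lies inside the band for baselines above 10^2.5 = 316 IU/mL, so the scale cannot be left open.
4. **Censoring.** The last available assessment. If the end of follow-up were read as the scheduled day, a patient last seen at Day 225 at the lowest value would be credited with 112 (to Day 337) or 168 (to Day 393) unobserved days.
5. **Report alongside.** The number of non-responders, the number with nadir at the last visit, and the from-nadir HBsAg duration as a secondary descriptive summary.

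The cost is SAP wording and re-derivation from data already collected. Durations will not be comparable with from-nadir figures, and non-responders leave the table. The 0.5-log cut is partly conventional: the SAP uses it as a category boundary, not as a response. The departure from the protocol's HBsAg wording must be recorded. Because SAP 17.2 describes interim analyses already done, it should also be stated that the cut was set after those looks.
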